# 1.5 SCHEDULE OF ACTIVITIES/VISITS (SOA) (PHASE III KENYA, ETHIOPIA, MOZAMBIQUE)

Procedures	Pre- screening (up to 3 months prior	Study Visit 0 Screening Day -7 to -1	Study Visit 1 Enrolment/ Baseline Day 0	Study Visit 2/ Day 1	Study Visit 3 Day 2	Study Visit 4/ Day 3	Study Visit 5/ Day 7	Study Visit 6 Day 21+/-7 day post treatment	Unscheduled	Withdrawal
Informed consent n	Х	Х								
Informed assent°	X	Χ								
Stool collection kit delivered		Χ						X		
Stool collection p		Χ						X		Χ
Stool analysis (Baermann and Kato-Katz) q		Χ						X		X
Inclusion and Exclusion criteria		Х	Х							
Demographics r		Χ								
Physical exam s		Χ	X					X	Χ	X
Vital signs t		Х	Х	Х	Х	Х	Х	Х	Χ	X
Height		Χ	X							
Weight		Χ	X							
Urine Pregnancy test u		Χ								
Haematuria strip test for Schistosoma h		Χ								
Serum HIV test v								X		
Randomization and treatment assignation			Х							
Study drug administration			Xw	X×	Χ y					
Study drug accountability			Χ	Х	Χ			Х		Χ
Concomitant medication & disease review		Х	Х	Х	Х	Х	Х	Х	Χ	Χ
Adverse event monitoring z		Χ	Х	Χ	Χ	Χ	Χ	Х	Χ	Χ
Complete Case Report Form (CRF)		Х	Х	Х	Х	Х	Х	Х	Χ	Χ

<sup>n Informed consent will be obtained from parents or guardians of all participants <18years. Informed consent/assent can be performed up to 3 months prior to screening visit as part of the pre-screening activities OR during screening visit.

 $^{\circ}$  Assent to participate in the trial will be obtained from participants 12-17 years old.

P A stool collection kit will be provided to participants for the collection of stool samples after providing assent and consent. The stool should be collected <24 h before examination for eligibility check. An aliquot of the collected stool sample will be stored for QC by PCR to confirm microscopic results from Kato-Katz and Baermann test if microscopy positive at screening and for all follow-up stool samples. Should technical issues arise or in case of discrepancy in results, an aliquot of the stool sample will be tested abroad for QC purposes.

<sup>q Lab tests will be performed on a fresh stool sample collected <24 hours before examination.

<sup>r Age, Date of Birth, Sex, Participant ID, Guardian relationship, age and contact details

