<sup>s Physical exam should include clinical diagnosis of scabies (rush/lesions on skin) before and after treatment. During unscheduled visits Physical exam will be performed only if necessary.

<sup>t Vital signs should Include heart rate, respiration rate, body temperature and blood pressure.

<sup>u A urine test kit will be provided in order to collect urine sample from all participants which will be examined by haematuria strip test as a proxy *for* Schistosoma and to confirm negative pregnancy test for female participants ≥12 years old or postmenarche.

Yerum HIV test will be offered only to eligible participants at the Manhiça site in Mozambique because of high HIV prevalence.

w Treatment Day 0. For all participants in Arms 1, 2 and 3. Treatment dose will be given under direct supervision.

\* Treatment Day 1. Only for participants in treatment Arm 3. Close observation for 3 hours post-treatment for safety evaluations.

<sup>y Treatment Day 2. Only for participants in treatment Arm 3. Close observation for 3 hours post-treatment for safety evaluations.

<sup>2 Adverse events will be assessed by direct observations of the study physician, or reported by the subject or parent/guardian.

Version 4.0 21st January 2022

ALIVE Study

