#### **Screening Phase**

The purpose of the screening phase is to confirm participant eligibility for enrolment in the study based on the inclusion and exclusion criteria. The objectives, procedures of the study, risks and requirements of

Version 4.0

the study will be explained to each potential participant and to their parent/guardian or their legal representatives. Section 10.1.1.2 describes the consent procedures. Considering the context in which the clinical trial is carried out, in many cases, group meetings with the parents/guardians of the potential participants must be organized in the community before screening as part of the informed consent process. For logistical reasons the informed consent and assent process can be performed up to 3 months

prior to the screening visit as part of the pre-screening activities or at the latest during the screening visit

If they accept to participate in the study, the participant, parent (guardian of the participant) or legal representative will be asked to sign a written informed consent form and the participant (12 - 17 years of age) an assent form before any study-specific procedures are conducted.

The following laboratory tests will be performed at screening after written consent and assent have been obtained:

- STH diagnostic test by Kato-Katz and Baermann (stool sample): For this, the participants will be provided with a stool collection kit to provide fresh stool (collected <24h before laboratory examination). The stool sample will be tested in the laboratory as part of the eligibility criteria. On obtaining the laboratory results, participants with a positive egg count for ONLY *A. lumbricoides*, but not for other STH as per the eligibility criteria, will not be eligible and shall be referred to the appropriate health care system for further evaluation, follow-up, and care.
- All participants with other helminth eggs which do not fulfil eligibility criteria or those with only
  Ascaris will be referred to the appropriate health care system for further evaluation, follow-up
  and care.

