- Urine pregnancy and haematuria strip test as proxy for *Schistosoma*: A urine kit will be provided in order to collect urine sample during the screening visit to test for pregnancy and to detect haematuria as a proxy for *S. haematobium*. Participants with haematuria shall be referred to the appropriate health care system for further evaluation, follow-up, and care. These participants will be included in the trial if they fulfil eligibility criteria.
- Sero-HIV test (finger prick for blood). This will only be offered for participants in Mozambique.
   HIV serostatus will be assessed to evaluate HIV infection as a possible covariate, due to the high

before any trial procedure is performed.

Version 4.0

ALIVE Study

21st January 2022

prevalence of HIV in the country but will not determine the participant's eligibility. In Kenya and Ethiopia, the low HIV prevalence does not justify HIV testing.

At each study site, a screening and enrolment log will be used to document all participants considered for enrolment regardless of whether they were enrolled or not. The screening and enrolment log will not contain names or other identifying information. A subject identification log will also be recorded to document identification of study participants enrolled in the trial in case follow-up is required. It is a CONFIDENTIAL list to be retained ONLY at the study site.

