5.1.5 Handling of missing data

Every effort will be made to minimise the amount of missing data in the trial. Information on the reason for missing data will be obtained, whenever possible.

Baseline demographic data

For missing data on age, gender, height and weight at baseline, multiple imputation will be performed. **Efficacy data**

For the efficacy analysis, the worst-case scenario will be considered, where participants with missing data will be considered as treatment failures. In such a case it will be assumed that all participants with no egg count data at day 21 will have the same egg count as at baseline.

Adverse Events

The following imputation rules for missing or partial AE start dates are used:

- If only Day is missing, the start day will be the first day of the month or the date of study drug first dose if the AE end date is on/after the date of study drug first dose or is missing/partial AND the start year and month of the AE are the same as year and month of the study drug first dose date;
- If Day and Month are both missing, the start date will be January 1 of the year or the date of study drug first dose if the AE end date is on/after the date of study drug first dose or is missing/partial AND the start year of the AE is the same as year of the study drug first dose date;
- If Day, Month, and Year are all missing, the date will not be imputed. However, if the AE end date is on/after the date of study drug first dose, then the AE will be considered a TEAE.

The missing or partial AE stop data will not be imputed.

If the severity of an AE is missing, it will be classified as "severe" in the summary tables by severity. If the assessment of relationship of study drug is missing, it will be classified as "related" to the study drug.

Concomitant Medications

The same imputation rule as AE start date imputation will be used for missing or partial start dates of medications.

The missing or partial medication stop data will not be imputed.

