5.2.3 Demographics and baseline characteristics

Demographics and other baseline characteristics will be summarized using the ITT population. The demographics characteristics will include age groups (school-age children (5 to 14 years-old) and young adults (15 to 18 years-old), gender, weight, height, body mass index (BMI). Other baseline characteristics will include photophobia, blurred vision, visual impairment, pruritus, skin lesions compatible with scabies, serum HIV test (Mozambique only), body temperature, blood pressure, heart rate, respiratory rate.

The baseline parasitological testing results, including number and percentage of participants who are positive for *Trichuris trichiura*, *Ascaris lumbricoides*, Hookworm, Haematuria, *Strongyloides stercoralis* will be presented.

Bivariate analysis of baseline demographics characteristics between screen failure participant and randomized participant may be presented.

Individual demographics and baseline characteristics will be listed.

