Cure rates will be also calculated by qPCR. For this, a participant is considered cured if the mean Ctvalues are less or equal than 40 at baseline, and greater than 40 after treatment. When there are nondetectable levels of DNA in the sample, it will be categorized with a Ct-value equal to 50. Cochran– Mantel–Haenszel (CMH) test, controlling the effect of site if that is appropriate (sufficient participants), will be used to compare the cure rates for the 3 treatment groups. In addition, Kappa test and the Fisher 's exact test or chi - square test will be used to compare the CR obtained by Kato-Kats and PCR for the same treatment arm.

Correlation between Kato-Katz counts and qPCR Ct-values will be explored through Pearson's or Spearman's (according to the underlying distribution) correlation tests. Different regression methods to predict EPGs based on Ct-values will be explored.

Increases in Ct-values after treatment will be considered as a reduction in parasite load. To measure whether the increase in ct is significant in each treatment arm, the "Wilcoxon signed-rank test" will be used.

The qPCR will allow the identification of hookworm species (*N. americanus* and *A. duodenale*), so it will be evaluated if there are differences in the response to treatment for these species. Kappa test will be used for the evaluation of both tests in the calculation of CR.

Relevant covariates will also be included in the data analysis. Particularly, HIV infection will be assessed as a covariate in participants recruited in Mozambique.

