5.4.3 Sub-group analyses

Subgroup analyses will be performed for the primary efficacy outcome on the ITT population. The variables for the subgroup analysis will include:

- Ivermectin drug exposure: categorized by >400 μg/Kg vs ≤400 μg/Kg
- Age: categorized by school-age children (5 to 14 years-old) & young adults (15 to 18 years-old).
- Co-infection: categorized by mono-infected vs co-infected
- Infected with HIV vs no infected with HIV
- Worm burden: categorized by WHO categories of egg burden categories measured by Eggs Per Gram (EPG) through Kato-Katz method [14]:

Species	Light	Moderate	Heavy	
T. trichiura	1 – 999	1000 – 9999	≥10000	
Hookworms	1 – 1999	2000 – 3999	≥4000	
A. lumbricoides	1 - 4999	5000 - 49999	≥50000	

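### The protocol's phase III schedule marks the HIV test at Visit 6 only, against protocol 8.1 and SAP Table 2; if followed, it leaves the SAP's HIV analyses without a baseline value and restricts them to children who attend Visit 6

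*Protocol*

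**What the plan says.** Three places give a time for the HIV test.

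- **Protocol 1.5 (phase III schedule).** The row "Serum HIV test" has one mark, under Visit 6. Screening, Visit 1 and Withdrawal have none. The footnote limits who is tested: "HIV test will be offered only to eligible participants at the Manhiça site in Mozambique because of high HIV prevalence".
- **Protocol 8.1, Screening Phase.** The list opens with "The following laboratory tests will be performed at screening after written consent and assent have been obtained", and one of its items is "Sero-HIV test (finger prick for blood). This will only be offered for participants in Mozambique". The section adds that the result does not decide eligibility.
- **SAP Table 2.** The same row is marked at Visit 0 and Visit 1, with nothing at Visit 6.

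The SAP uses the result in three ways. Section 5.2.3 includes "serum HIV test (Mozambique only" among the baseline characteristics. Section 5.4.1 states: "Particularly, HIV infection will be assessed as a covariate in participants recruited in Mozambique". Section 5.4.3 lists "Infected with HIV vs no infected with HIV" as a subgroup of the primary efficacy outcome in the ITT population. The protocol has the covariate (9.5.3), but HIV is not in its own subgroup list (9.5.7).

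Three other SAP rules matter here. Section 5.1.2 defines baseline, unless otherwise specified, as the latest value before the first dose. Sections 4.1 and 5.1.5 count participants without efficacy data as failures. On missing baseline data, 5.1.5 says: "For missing data on age, gender, height and weight at baseline, multiple imputation will be performed". HIV is not named there.

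**The concern.** The schedule of activities is what sites work from; protocol 8.2 refers them to it for study procedures. A site that follows the protocol's table would draw the HIV sample at the outcome visit. Two problems would follow.

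First, the result would come after dosing, so it would not meet the SAP's definition of baseline. Read strictly, the baseline HIV variable would be empty whatever the loss to follow-up.

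Second, if the Visit 6 result is used anyway, knowing a child's HIV status depends on attending the visit that measures the outcome. A Mozambican child who misses Visit 6 would have no HIV status and, without a withdrawal stool result, would also be an ITT failure. The HIV subgroup, planned on the ITT population, would lose failures that the primary analysis keeps. The covariate analysis would lose the same children. HIV status not collected before a child is lost cannot be recovered later.

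**Working it through.** **1. Is the mark really at Visit 6?** In the protocol 1.5 table the single HIV mark stands in the same column as the follow-up mark in the stool collection and stool analysis rows, which is Visit 6. The stool rows also have a mark under Withdrawal; the HIV row does not. The position does not look like an extraction fault.

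**2. The three sources side by side**

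| Source | Screening (Visit 0) | Baseline (Visit 1) | Visit 6 | Withdrawal |
|---|---|---|---|---|
| Protocol 1.5, HIV | no | no | yes | no |
| Protocol 8.1, HIV | yes | not stated | not stated | not stated |
| SAP Table 2, HIV | yes | yes | no | no |
| Protocol 1.5, stool | yes | no | yes | yes |

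Protocol 8.1 and SAP Table 2 are compatible, since both place the test before dosing. One schedule row disagrees with two other places. The remark in 8.1 that the result does not affect eligibility also fits a test done before enrolment. No section gives a reason for Visit 6.

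**3. The plan's own figures.** Inputs from protocol 9.2 are T. trichiura cure rates of 23.7% (ALB), 43.7% (FDC) and 59% (FDCx3); evaluable numbers of 116, 223 and 223; 10% loss; and a two-sided alpha of 0.05/3 = 0.0167.

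- Inflation, N/(1 - 0.10): 116/0.9 = 128.9, giving 129; 223/0.9 = 247.8, giving 248. Both match the plan.
- Power (two proportions, pooled variance): 90.6%, 100.0% and 80.2%, against the stated 91%, 100% and 80%. They reproduce, and nothing in this point changes them.

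**4. Illustration of the attendee restriction.** Assume loss d equal across arms, no withdrawal stool results, and the planned cure rates among those seen at Visit 6. Then the ITT rate is (1 - d) x the attendee rate. With d = 0.10:

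| | Attendees | ITT, missing = failure |
|---|---|---|
| ALB | 23.7% | 0.9 x 23.7 = 21.3% |
| FDC | 43.7% | 0.9 x 43.7 = 39.3% |
| FDCx3 | 59.0% | 0.9 x 59.0 = 53.1% |
| FDC - ALB | 20.0 points | 0.9 x 20.0 = 18.0 points |
| FDCx3 - ALB | 35.3 points | 0.9 x 35.3 = 31.8 points |

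For d from 5% to 15%, the ITT differences run from 19.0 to 17.0 points (FDC - ALB) and from 33.5 to 30.0 points (FDCx3 - ALB). The attendee differences stay at 20.0 and 35.3.

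**5. How many children?** The documents give no Mozambique enrolment. If Mozambique supplied 20%, 33% or 50% of the 499 phase III T. trichiura participants (assumed shares), 10% loss would leave about 10, 17 or 25 of them without HIV status. On the whole phase III total of 1097 the figures would be about 22, 37 or 55. If the test is done before dosing, loss before Visit 6 causes none.

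**The case against.** Two of the three places, including the SAP that governs the analysis, already put the test before dosing. If the site follows those, nothing is lost. This stands, and it makes the consequence conditional.

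Several stronger readings are tempting, and the documents do not support them:

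- **Every child lost before Visit 6 has no HIV status.** Testing is offered only in Mozambique, can be declined, and under protocol 8.1 or SAP Table 2 would already have been done.
- **All such children are ITT failures.** The Withdrawal column includes stool collection and analysis, and protocol 8.1 asks for every effort to complete final assessments in early leavers. Only those without efficacy data are counted as failures.
- **They necessarily drop out of the HIV analyses.** The SAP's imputation list omits HIV, but protocol 9.5.8 allows multiple imputation if needed and names no variables.
- **Attendee analysis inflates the treatment effect.** In the illustration the attendee rates are the plan's expected rates, and the missing-as-failure rule pulls the ITT rates down. Cure-rate ratios are the same in both (43.7/23.7 = 39.3/21.3 = 1.84). The illustration shows a change of population and estimand. It does not establish bias between arms, which would need unequal loss, and the documents give no figure for that.
- **Visit 6 was a deliberate design choice.** No rationale appears, and protocol 8.1 contradicts it.

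It can also be said that HIV serostatus will seldom change over about a month, so a late result is a fair stand-in. That helps for children tested at Visit 6. It does nothing for those who never attend, and the SAP's baseline definition still excludes the result.

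**Conclusion.** The point holds as a contradiction between documents with a conditional analytic consequence. Protocol 1.5 conflicts with protocol 8.1 and SAP Table 2, and its timing cannot supply the baseline HIV value that the SAP requires. If the Mozambique site follows protocol 1.5, the HIV subgroup and covariate analyses become analyses of Visit 6 attendees, although the subgroup is specified for ITT.

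The shifts of 2.0 points (18.0 to 20.0) and 3.5 points (31.8 to 35.3) are only an illustration. They apply whole-trial planning rates to one site and assume equal 10% loss and no withdrawal stool results. The number of children affected cannot be derived from the documents.

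A reader might infer that the primary result is at risk. It is not: the main CMH comparison controls for site where appropriate and does not use HIV, and no sample size or power figure changes. The schedule is wrong as written and should be corrected, but the stake is limited to the HIV analyses.

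**What to change.** - **Protocol 1.5:** move the HIV mark from Visit 6 to Visit 0/Visit 1, before dosing, so that it agrees with protocol 8.1 and SAP Table 2.
- **Reporting:** if any HIV results were obtained only at Visit 6, present the analyses that use them as attendee analyses, not as baseline or ITT analyses. The documents do not show which schedule the site used, so this should be checked.
- **SAP 5.1.5:** add a sentence on missing or declined HIV status. The test is optional, so some gaps will remain whatever the visit.

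Cost: the test and the children offered it stay the same, so no procedure is added. It is a correction to the protocol schedule, and under protocol 10.1 an amendment needs ethics approval before it takes effect. Some children tested before dosing will later be lost to follow-up.

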# 2 INTRODUCTION

#### 2.1 STUDY RATIONALE

This clinical trial focuses on the search of new broad spectrum therapeutic approaches for the treatment of soil transmitted helminths (STH) for use in preventive chemotherapy (PC) through mass drug administration (MDA), as designed by the World Health Organization WHO(1). PC is defined by WHO, as a pharmacological intervention for the treatment of communities in order to prevent morbidity caused by the infections, but not as a means of preventing the acquisition of the infection. This trial will generate evidence-based information for decision making, WHO pre-qualification and the registration of a new anthelminthic co-formulation for the drug and medicines agencies in Africa and Europe (European Medicines Agency (EMA)).

STH are a group of diseases that include *Ascaris lumbricoides, Strongyloides stercoralis, Trichuris trichiura* and the hookworms: *Ancylostoma duodenale* and *Necator americanus*. Despite differences in their clinical syndromes and mechanisms of infection, they are all transmitted in areas with inadequate water and sanitation and hygiene measures. More than a quarter of the world's population is at risk of infection with STH. These diseases are the most prevalent of all Neglected Tropical Diseases (NTDs) worldwide and disproportionately affect impoverished populations, causing significant morbidity in pre-school and school age children(2). The 2015 Global Burden of Disease (GBD) study ranks STH as the NTD that poses the greatest burden of years lived with disability (YLD), with an estimation of 3.17 million years (3).

Currently, available treatments against STH are the benzimidazole drugs, albendazole (ALB) and mebendazole (MBZ), in single dose regimens because of their safety, efficacy and availability through drug donation from their manufacturers. Although the efficacy of ALB against *A. lumbricoides* remains above 90%, the efficacy against other STH species is estimated as 80% (95% CI: 72-86%) for hookworms and 31% (95% CI: 21-43%) for *T. trichiura* (4). It is particularly alarming that the efficacy against *T. trichiura* has decreased from 30% to 15% in the last 16 years (4). In addition, the currently recommended regimens against STH have very low efficacy against *S. stercoralis* (5), which remains largely untreated with the current WHO strategy. Given this situation, there is a pressing need to identify regimens with improved

Version 4.0

ALIVE Study 21st January 2022

efficacy and provide evidence for the revision of the current strategy, if transmission interruption goals are to be achieved (6,7).

The use of combination therapy with existing drugs against STH has been identified as a strategy that could offer a solution to the drawbacks and risks of the current strategy of monotherapy. Among them, the use of ALB-IVM has several advantages:

- a. Vast experience in its use for the treatment of lymphatic filariasis (LF), with millions of individuals treated (8), without safety or drug interaction issues of clinical relevance.
- b. Improved efficacy against *T. trichiura* and *S. stercoralis* (9,10).
- Decreased risk of emergence of drug resistance due to the different mechanisms of action of the
   2 components of the regimen (11,12).
- d. Extended anti-parasitic spectrum with opportunities for integration with other NTD control programs (LF, scabies) and possibly malaria vector control (13).

As a reflection of the above-mentioned advantages, the WHO recently incorporated IVM to its list of essential drugs for the treatment of STH (14), and an expert panel gathered by the Bill & Melinda Gates Foundation identified ALB + IVM as the combination therapy to be explored in priority (15).

